**Historical control:**

1. Age  $\geq$  18 years
2. Received a lung or heart-lung transplant at NYU Langone Health
3. Completed one year from transplant on IR tacrolimus

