## **10.3 Analysis Datasets**

All subjects will be entered into a database containing de-identified information. All patients who take one dose of the study drug will be included in the safety analyses (intention-to-treat). However, only patients completing the full first year post-lung transplant will be included in the efficacy analysis (per-protocol analysis).

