## **10.4 Description of Statistical Methods**

### **10.4.1**

#### **General Approach**

The study is a two-arm, non-randomized study comparing a prospective arm of patients receiving Envarsus XR to a historical control who received IR tacrolimus. Descriptive statistics will be used for baseline characteristics and to compare nominal outcomes such as de novo DSA and the incidence of CLAD at 1 year post-transplant. These data will be presented as frequencies and will be compared using Chi-square tests or Fishers exact test, as appropriate. The primary outcome freedom from ACR will be compared using Kaplan-Meier survival analysis and analyzed with the log-rank test. Continuous data will be presented as median (interquartile range) and compared using Mann-Whitney U test. A two-tailed P value of < 0.05 will be considered as significant for inferential tests.

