### **10.4.2**

#### **Analysis of the Primary Efficacy Endpoint(s)**

The primary endpoint, percentage of patients remaining on Envarsus XR at 1-year, will be measured as a single endpoint on a nominal scale. It will be analyzed using descriptive statistics.

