### **10.4.3**

#### **Analysis of the Secondary Endpoint(s)**

1. Freedom from ACR will be compared using Kaplan-Meier survival analysis and the log-rank test.
2. Composite rejection standardized score at 1 year follow-up will be presented as median (IQR) and will be compared using the Mann-Whitney U test
3. Treated episodes of rejection will be presented as frequencies and compared using chi-square test
4. Incidence of CLAD at 1 year will be presented as odds ratio with 95% confidence intervals and compared between groups using logistic regression.
5. Incidence of *de novo* DSA at 1 year will be presented as odds ratio with 95% confidence intervals and compared using between groups using logistic regression.
6. Mortality a 1 year post-transplant will be compared using Kaplan-Meier survival curves and log-rank analysis.

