### **10.4.4**

#### **Safety Analyses**

Safety endpoints include worsening chronic kidney disease and discontinuation of therapy will be analyzed as changes from baselines and summary data during the course of treatment, respectively. These will be compared as linear regression and frequencies using the chi-square test, respectively. All AEs will be ascertained and reported by the PI.

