#### **10.5 Sample Size**

We plan to prospectively enroll 40 patients into the Envarsus XR arm to provide a 2:1 sample size with a historical control of patients who received IR tacrolimus. The sample size of 40 patients for the Prospective Cohort was chosen based on the expected number of lung transplants performed in one year at NYULH. The Historical Control Cohort sample size includes all patients who were transplanted at NYULH and completed one year of follow-up post lung transplant while maintained on IR tacrolimus. The 2:1 sample size was chosen as the purpose of the study is to gain experience with Envarsus XR in lung transplant recipients and IR tacrolimus has many years of clinical use. As this is a pilot study, there will be no power calculations.

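### Historical controls must have completed a year on IR tacrolimus, so their deaths and discontinuations are 0/20 by eligibility and between-arm tests of those outcomes cannot be interpreted

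*Combined protocol and SAP*

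**What the plan says.** Control eligibility (Section 5.1, historical control, item 3) requires that the patient "Completed one year from transplant on IR tacrolimus". Section 10.5 says the same of the cohort as a whole: it "includes all patients who were transplanted at NYULH and completed one year of follow-up post lung transplant while maintained on IR tacrolimus". The prospective arm carries no such condition; its patients need only be able to convert within the first month after transplant.

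Section 10.3 defines two analysis sets. For safety: "All patients who take one dose of the study drug will be included in the safety analyses (intention-to-treat". For efficacy: "only patients completing the full first year post-lung transplant will be included in the efficacy analysis (per-protocol analysis".

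One-year survival is a secondary endpoint (Section 4.2.2). Under Section 10.4.3, item 6, mortality "will be compared using Kaplan-Meier survival curves and log-rank analysis". Section 10.4.4 names worsening chronic kidney disease and discontinuation of therapy as safety endpoints and says: "These will be compared as linear regression and frequencies using the chi-square test, respectively". Section 10.4.1 describes a two-arm comparison with two-tailed significance at 0.05. The primary endpoint, the percentage still on Envarsus XR at one year, has no comparator: "It will be analyzed using descriptive statistics".

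**The concern.** The control entry criterion is itself the outcome being compared. A recipient who died in the first year, or came off IR tacrolimus, is not eligible as a control. The Envarsus XR arm is assembled at conversion, and its patients can still die or stop. This differs from the ordinary confounding of a historical comparison, where the control outcome is imperfect but informative. Here it is fixed in advance and carries no information, and a larger sample would not help.

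Survival and drug discontinuation are where readers will look for safety. They could take a significant difference as harm from Envarsus XR, or a non-significant one as reassurance. The design supports neither conclusion.

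**Working it through.** **Inputs.** 40 Envarsus XR and 20 control patients (Protocol Summary; Section 10.5); two-sided 0.05 (Section 10.4.1); control events fixed at 0/20 (Sections 5.1 and 10.5). The plan gives no power figure or event rate to reproduce. The true rates below are assumptions, set equal in the two formulations so that any rejection is false.

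**Mortality, by analysis set.**

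- Section 10.3 completers: a patient who died in the year is in neither arm. There are 0 deaths against 0, and the log-rank statistic is undefined.
- All dosed patients: deaths can occur only in the Envarsus XR arm. With no control deaths, no censoring before one year and untied deaths, the control risk set stays at 20. Before death number i+1 the Envarsus XR risk set is r = 40 − i. Each death adds r/(r+20) to the expected count E and 20r/(r+20)² to the variance V.
  - 7 deaths: E = 4.541, V = 1.594; (7 − 4.541)²/1.594 = 3.79, p = 0.051.
  - 8 deaths: E = 5.163, V = 1.829; (8 − 5.163)²/1.829 = 4.40, p = 0.036.

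Eight Envarsus XR deaths are therefore enough for significance.

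**Discontinuation, k/40 against 0/20.** The uncorrected chi-square is 60(20k)² / [40·20·k·(60 − k)] = 30k/(60 − k). The continuity-corrected form is 60(20k − 30)² / [40·20·k·(60 − k)].

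| Test | Last non-significant k | First significant k |
|---|---|---|
| Uncorrected chi-square | 6: 3.33, p = 0.068 | 7: 3.96, p = 0.047 |
| Fisher exact | 7: p = 0.084 | 8: p = 0.043 |
| Continuity-corrected chi-square | 9: 3.68, p = 0.055 | 10: 4.34, p = 0.037 |

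At 7/40 against 0/20 the smallest expected count is 7 × 20/60 = 2.33, so Fisher's test is the sensible choice. Section 10.4.1 allows it for nominal outcomes, which "will be compared using Chi-square tests or Fishers exact test, as appropriate". Section 10.4.4 names only chi-square.

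**Probability of a false finding against Envarsus XR.** This is P(X ≥ k) with X ~ Binomial(40, p), where p is the assumed true rate in both formulations.

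| Test (threshold) | 5% | 10% | 15% | 20% | 25% |
|---|---|---|---|---|---|
| Fisher (k = 8) | 0.001 | 0.042 | 0.244 | 0.563 | 0.818 |
| Uncorrected chi-square (k = 7) | 0.003 | 0.100 | 0.393 | 0.714 | 0.904 |
| Continuity-corrected (k = 10) | <0.001 | 0.005 | 0.067 | 0.268 | 0.561 |

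The log-rank test in all dosed patients shares the Fisher threshold of 8, so equal true mortality of 5, 10, 15 or 20% gives a false finding of harm with probability 0.001, 0.042, 0.244 or 0.563.

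**Comparison with unselected controls.** Replacing the fixed 0/20 by Binomial(20, p) and enumerating all outcomes, the total rejection rate for p from 5% to 25% is 0.040 to 0.050 (uncorrected), 0.015 to 0.035 (Fisher) and 0.003 to 0.023 (corrected). These sizes count both directions. Against a fixed zero every rejection goes one way, so comparing like directions would only widen the gap. Twenty unselected controls would show no event with probability (1 − p)²⁰: 0.358, 0.122, 0.039, 0.012 and 0.003 at the five rates.

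**Bias in the estimate.** The expected difference is p − 0 where the truth is p − p = 0, so the bias equals the true control rate whatever the p value.

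**The case against.** Five points can be made for the plan.

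- **Section 10.4.4 names no groups, and the safety set is defined by a dose of the study drug, which controls never took.** True. Still, a chi-square comparison needs groups, and Section 10.4.1 describes a two-arm study. If a between-arm test is not intended, the text should say so.
- **Mortality is listed as a secondary endpoint, so the more literal reading puts it in the completer set. There Section 10.3 alone empties the test, whatever controls are used.** This stands. Section 10.3 shares responsibility with Section 5.1, and the false-harm figures for mortality belong to the all-dosed reading only. They also assume all 40 are enrolled, which Section 10.4.7.1 does not assure because any death halts further enrolment. Neither reading gives a usable test.
- **The large error rates need assumed rates of 15% or more.** This also stands. Under Fisher's test the false-positive rate passes 5% only when the true rate exceeds about 10.4%, and at 5% all three tests almost never reject. The estimate is still biased by 5 points there, and a null result would be false reassurance.
- **Equal discontinuation is a doubtful benchmark.** Section 2.1 says the site has been converting recipients to Envarsus XR after discharge, so many stops of IR tacrolimus may be practice switches and not intolerance. This limits what a repaired comparison could show. It does not make the present one valid.
- **It is an unpowered pilot with a descriptive primary endpoint.** The primary endpoint is indeed untouched. But the plan chose inferential tests for these outcomes, and the fault is not one of power.

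**Conclusion.** The concern holds. Control deaths and discontinuations are 0/20 by eligibility, and nothing in the plan corrects for this. The mortality test is either empty (completers) or able to point only against Envarsus XR (all dosed). The discontinuation difference, on the natural between-arm reading, is biased against Envarsus XR by the full true control rate. At assumed equal discontinuation rates of 10 to 25%, the false-positive probability is 4 to 82% by Fisher's test and 10 to 90% by uncorrected chi-square. At 5% it is negligible, but the bias remains.

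The primary endpoint is unaffected. ACR, CLAD and de novo DSA are affected less, because Section 10.3 also restricts the Envarsus XR efficacy set to one-year completers. The asymmetry left there is that controls must also have stayed on their drug, which Section 10.3 does not clearly require of Envarsus XR patients. This must be fixed, because a named secondary endpoint and a named safety endpoint have planned tests that cannot be interpreted.

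**What to change.** **Simplest change.** Delete the between-arm log-rank test of mortality (Section 10.4.3, item 6) and the between-arm chi-square test of discontinuation (Section 10.4.4). Report 1-year survival and discontinuation, with reasons, for all dosed Envarsus XR patients with 95% confidence intervals. State that the control values are 100% and 0% by eligibility. This needs no new data.

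**Alternative, only if a comparison is wanted.** Amend Sections 5.1, 10.3 and 10.5 together:

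1. Take as controls all consecutive adult lung or heart-lung recipients in a stated calendar window who were alive, on IR tacrolimus and able to take oral medication at a landmark within the first month that matches the prospective criterion. Keep them whatever happens later.
2. Use one time zero for both arms. At present the Envarsus XR schedule starts at first dispensation (Section 20), while the control year runs from transplant.
3. Analyse mortality and the time-to-event outcomes in all such patients, not in completers. Changing Sections 5.1 and 10.5 but leaving Section 10.3 would still remove control deaths.

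The alternative costs further retrospective chart review and may give a control number other than 20. It may also bring in many controls who later moved to Envarsus XR; those switches should be reported separately from stopping for intolerance. Neither option needs extra prospective enrolment.

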### **7.2.2** **Control Cohort**

### **Retrospective data to be collected in the Historical**

Specific data pertaining to primary and secondary outcomes to be collected in the Historical Control Cohort is the same as listed above in the Prospective Cohort and at the same time points.

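### If the historical cohort is the comparator, the chi-square test of discontinuation is uninformative: control entry fixes lasting discontinuation at 0/20, so Envarsus XR can only tie or look worse

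*Combined protocol and SAP*

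**What the plan says.** **Who can be a control.** Section 5.1 requires that a historical control has "Completed one year from transplant on IR tacrolimus". Section 10.5 repeats the condition: the cohort consists of patients who finished a year of follow-up while maintained on that drug. The prospective arm has no matching condition. Its patients need only be able to convert within the first month.

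**What is tested.** Section 10.4.4 names two safety endpoints, worsening chronic kidney disease and discontinuation. It says that these and "discontinuation of therapy will be analyzed as changes from baselines and summary data during the course of treatment, respectively". It continues: "These will be compared as linear regression and frequencies using the chi-square test, respectively". Taking each 'respectively' in order, discontinuation is summarised as frequencies and compared by chi-square. The section does not say between whom.

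**Who might be compared.** Section 10.4.1 states: "The study is a two-arm, non-randomized study comparing a prospective arm of patients receiving Envarsus XR to a historical control who received IR tacrolimus". It also provides for nominal outcomes to be "compared using Chi-square tests or Fishers exact test, as appropriate", and sets a two-tailed P below 0.05 as significant. Section 10.3 defines the safety set: "All patients who take one dose of the study drug will be included in the safety analyses".

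**Sizes.** The Protocol Summary gives 40 Envarsus XR patients and 20 controls. No discontinuation rate is given for either drug.

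**The concern.** The control entry rule uses the outcome that section 10.4.4 then tests. A recipient who left IR tacrolimus for good during the year cannot be a control, so the control count of lasting discontinuations is zero before any chart is opened. The word 'lasting' matters: a temporary interruption followed by a return to IR tacrolimus could still qualify.

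Leaving IR tacrolimus does happen at this centre. Section 2.1 describes routine conversion to Envarsus XR after discharge, partly because of fewer side effects. Those conversions need not all be safety events, but the entry rule removes any that were.

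Two misreadings are at stake. A significant result would be read as a safety disadvantage of Envarsus XR, although the eligibility rule could have produced it. A non-significant result would be read as similar tolerability, although the IR tacrolimus rate never entered the comparison.

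**Working it through.** **Inputs.** Envarsus XR n = 40 and controls n = 20 (Protocol Summary; section 10.5 gives the 2:1 ratio, and 40/20 = 2). Alpha is 0.05 two-sided (section 10.4.1). Control discontinuations are 0, by section 5.1. Envarsus XR discontinuations are x. The plan has no power or error figure for this test to reproduce, and section 10.5 says that none was calculated.

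**Step 1. Smallest x that gives P<0.05 against 0/20.**

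Uncorrected chi-square for the table [x, 40−x; 0, 20] is 60(20x)² / [40·20·x·(60−x)] = 30x/(60−x).
- x = 6: 180/54 = 3.33, P = 0.068.
- x = 7: 210/53 = 3.96, P = 0.047.

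With Yates correction the statistic is 60(20x−30)² / [800·x·(60−x)].
- x = 9: 3.68, P = 0.055.
- x = 10: 4.34, P = 0.037.

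Fisher's exact test, two-sided, adds the probability of the observed table to those of all tables no more likely.
- x = 7: P = 0.084.
- x = 8: C(40,8)/C(60,8) = 0.0301 for the observed table, plus 0.0131 from the opposite tail. P = 0.043.

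The expected control count is 20x/60. It is 2.7 at x = 8 and does not reach 5 until x = 15, so Fisher is the suitable choice over the range that matters. Changing the test does not remove the fixed zero.

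**Step 2. Chance of a false finding against Envarsus XR when the two drugs are equal.** Let r be the true one-year discontinuation rate on both drugs. It is an assumption. With the control cell fixed at zero, X ~ Binomial(40, r), and the chance is P(X ≥ 8) for Fisher, P(X ≥ 7) for uncorrected chi-square and P(X ≥ 10) with Yates.

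| Assumed r | Fisher | Chi-square | Yates | Fisher, controls not selected on staying on drug |
|---|---|---|---|---|
| 5% | 0.07% | 0.3% | <0.01% | 0.03% |
| 10% | 4% | 10% | 0.5% | 0.5% |
| 20% | 56% | 71% | 27% | 1.7% |
| 30% | 94% | 98% | 80% | 1.6% |

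The last column lets the control count vary as Binomial(20, r) and counts only significant results against Envarsus XR.

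**Step 3. Chance of a result in favour of Envarsus XR.** It is zero at every rate, because no x gives a proportion below 0/20. The best outcome is 0/40 against 0/20, where chi-square is undefined. If the true rates were 20% on Envarsus XR and 30% on IR tacrolimus (both assumed), the test would call Envarsus XR worse with probability 56% and better with probability 0. With unselected controls the Fisher figures would be 0.2% and 10.5%.

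**Step 4. The other reading.** If section 10.3 is taken literally, only patients who took the study drug are in the safety set. Controls are then outside it, and section 10.4.4 specifies a comparison with one group.

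**The case against.** **The comparator is inferred.** A reader might take it as settled that the plan will test x/40 against 0/20. The documents do not go that far: section 10.4.4 names no comparator, and the safety set in section 10.3 is defined by taking the study drug. What supports the inference is the two-arm description and the verb 'compared'. Section 7.2.2 should not be added to this. It says "Specific data pertaining to primary and secondary outcomes to be collected in the Historical Control Cohort is the same as listed above", but the lists that it points to do not include discontinuation, which is a safety endpoint and not a primary or secondary one. This objection stands, so the point is conditional. It does not rescue the test, because the other reading leaves nothing to compare.

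**The large probabilities rest on assumed rates.** A reader might infer that a false signal is likely. The documents do not show that. The only lung data cited, in section 2.1, are 20 stable recipients followed for six months after conversion from another prolonged-release product, with no withdrawal required for a major adverse event. Those patients were stable and the follow-up was shorter, so this fixes no rate for the present trial, but it does not point to 20% or 30%. At 5% or 10% a false Fisher signal is unlikely and the test is merely uninformative. This also stands.

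**The consequence is limited.** This is a pilot, the error runs against the study drug, and the percentage remaining on Envarsus XR is already the primary endpoint, single-arm and descriptive under section 10.4.2. All true. Pilot status does not cover the problem, however, since section 10.4.1 keeps P<0.05 for inferential tests and a larger sample would not remove the zero.

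**Wider reach.** A reader might infer that the same rule biases ACR, DSA, CLAD and eGFR in a known direction, so that the control cohort must be rebuilt. The documents do not support that. Section 10.3 says that "only patients completing the full first year post-lung transplant will be included in the efficacy analysis (per-protocol analysis", which restricts the Envarsus XR arm to year completers as well, and the direction and size of any remaining bias are unknown.

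**Conclusion.** The point holds in conditional form. If the historical cohort is the comparator, as the wording of sections 10.4.1 and 10.4.4 implies, the chi-square test of discontinuation cannot inform about IR tacrolimus and can only tie or go against Envarsus XR. If it is not, the test has no comparator. Neither reading gives a valid result.

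The fixed zero and the thresholds (8/40 by Fisher, 7/40 by uncorrected chi-square, 10/40 with Yates) follow from the entry rule and the arm sizes. The false-signal chances, 0.07% to 94% by Fisher over assumed rates of 5% to 30%, depend wholly on those rates and on equal rates in both groups. The zero applies to lasting discontinuation only. The primary endpoint is not affected. The change should be made, but the trial's main result does not depend on it.

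**What to change.** 1. In section 10.4.4, delete the between-group chi-square for discontinuation and substitute: *Discontinuation of Envarsus XR will be reported for all patients who took at least one dose, as a percentage with an exact 95% confidence interval and the reason for each discontinuation. No comparison with the historical cohort will be made, because entry to that cohort required remaining on IR tacrolimus.*
2. In section 10.3, state that controls are not part of the discontinuation analysis.
3. Optionally, report how many recipients started on IR tacrolimus were left out of the control cohort because they switched or died.

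Items 1 and 2 cost a few sentences and lose no valid information. With 40 patients the replacement estimate would read, for example, 4/40 = 10% (2.8% to 23.7%), 8/40 = 20% (9.1% to 35.6%) or 12/40 = 30% (16.6% to 46.5%). Item 3 costs a count from existing records. No change to the control cohort is needed for this point.

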### 5.2 Exclusion Criteria

An individual who meets any of the following criteria will be excluded from participation in this study:

**Prospective arm:**

1. Contraindication to tacrolimus due to allergic or adverse reactions
2. Pregnant or nursing women

**Historical control:**

1. Contraindication to tacrolimus due to allergic or adverse reactions (not including chronic kidney disease)

### 5.3 Vulnerable Subjects

Vulnerable subjects will not be eligible for enrollment.

### 5.4 Strategies for Recruitment and Retention

Recruitment of patients in the Prospective Cohort will occur during routine evaluation visits to determine candidacy for a lung transplant at NYU Langone Health by a member of the study team. Patients will be informed of the option to enroll in this study, and if interested, detailed information pertaining to the risks and benefits of the trial will be provided. Historical control patients will be reviewed retrospectively because they have already completed the study period and thus will not require recruitment into the study.

No additional information about potential candidates will be collected to determine interest or candidacy for this trial than would otherwise be normally collected as per standard of care for evaluation for a lung transplant.

Written informed consent for enrollment in the study will occur once the patient has been listed for lung transplantation in a private patient clinic room. Timing of consent for enrollment in relation to transplant date will vary between patients as acuity of disease is variable and waiting time to transplant is unpredictable.

The target sample size for the Prospective Cohort is 40 patients with early conversion to Envarsus XR.

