## 3 Objectives and Purpose

### 3.1 Primary Objective

The primary objective will be to assess the feasibility of early conversion to Envarsus XR at 1-year follow-up.

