### 4.2 Study Endpoints

#### 4.2.1

#### Primary Study Endpoints

The primary endpoint will be percentage of patients remaining on Envarsus XR at 1-year follow-up.

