**Prospective arm:**

1. Age  $\geq$  18 years
2. Received a lung or heart-lung transplant at NYU Langone Health
3. Be able to convert to Envarsus XR within the first month post-transplant
4. Able and willing to provide informed consent

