### **5.6 Total Number of Participants and Sites**

Forty patients are expected to be enrolled and switched to Envarsus XR post-transplant. No sites outside of NYU Langone Health will enroll patients.

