## 8.3 Time Period and Frequency for Event Assessment and Follow-Up

The occurrence of an AE or SAE may come to the attention of study personnel during study visits and interviews of a study participant presenting for medical care, or upon review by a study monitor. All AEs including local and systemic reactions not meeting the criteria for SAEs will be captured on the appropriate RF. Information to be collected includes event description, time of onset, clinician's assessment of severity, relationship to study product (assessed only by those with the training and authority to make a diagnosis), and time of resolution/stabilization of the event. All AEs occurring while on study must be documented appropriately regardless of relationship. All AEs will be followed to adequate resolution.

Any medical condition that is present at the time that the participant is screened will be considered as baseline and not reported as an AE. However, if the study participant's condition deteriorates at any time during the study, it will be recorded as an AE. UPs will be recorded in the data collection system throughout the study.

Changes in the severity of an AE will be documented to allow an assessment of the duration of the event at each level of severity to be performed. AEs characterized as intermittent require documentation of onset and duration of each episode.

The PI will record all reportable events with start dates occurring any time after informed consent is obtained until 7 (for non-serious AEs) or 30 days (for SAEs) after the last day of study participation. At each study visit, the investigator will inquire about the occurrence of AE/SAEs since the last visit. Events will be followed for outcome information until resolution or stabilization.

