## 20 Schedule of Events

Activity	Screening Visit (POD 0 to30)	SVD0*	SVW1 (+/- 5 days)	SVW2 (+/- 5 days)	SVW3 (+/- 5 days)	SVW4 (+/- 5 days)	SVW5 (+/- 5 days)
Study team procedures							
Consent	X						
Medical History	X						
Physical Exam	X						
Height	X						
Weight	X						
Vitals signs	X						
Review all recipient inclusion/exclusion criteria	X						
Study drug dispensation		X					
Participant study drug compliance check and accountability						X	
Bronchoscopy with biopsy						X	
Spirometry (FEV1)						X	
Donor-specific antibody						X	
Laboratory Evaluations							
Biochemistry			X	X	X	X	X
Hematology			X	X	X	X	X
Tacrolimus Co			X	X	X	X	X

SVD=study visit day; SVW=study visit week

\*Study visit day 0 = day of first drug dispensation and may occur on the same day as screening visit.

\*For SVW4 and SVW12: Bronchoscopies and DSAs will be done per SOC and as close to the specified study visit week as possible with a window of +/- 14 days.

CONFIDENTIAL

This material is the property of the NYU School of Medicine and Langone Medical Center. Do not disclose or use except as authorized in writing by the study sponsor

Activity	SVW6 (+/- 5 days)	SVW7 (+/- 5 days)	SVW8 (+/- 5 days)	SVW9 (+/- 5 days)	SVW10 (+/- 5 days)	SVW11 (+/- 5 days)	SVW12 (+/- 5 days)
Study team procedures							
Participant study drug compliance check and accountability			X				X
Bronchoscopy with biopsy							X
Spirometry (FEV1)			X				X
Donor-specific antibody							X
Laboratory Evaluations							
Biochemistry	X	X	X	X	X	X	X
Hematology	X	X	X	X	X	X	X
Tacrolimus C 0	X	X	X	X	X	X	X
Activity	SVW16 (+/- 5 days)	SVW20 (+/- 5 days)	SVW24 (+/- 5 days)	SVW28 (+/- 5 days)	SVW32 (+/- 5 days)	SVW36 (+/- 5 days)	SVW40 (+/- 5 days)
Study team procedures							
Participant study drug compliance check and accountability	X	X	X	X	X	X	X
Bronchoscopy with biopsy			X				
Spirometry (FEV1)	X	X	X	X	X	X	X
Donor-specific antibody			X			X	
Laboratory Evaluations							
Biochemistry	X	X	X	X	X	X	X
Hematology	X	X	X	X	X	X	X
Tacrolimus C 0	X	X	X	X	X	X	X

Activity	SVW44 (+/- 5 days)	SVW48 (+/- 5 days)	SVW52 (+/- 5 days)
Study team procedures			
Participant study drug compliance check and accountability	X	X	X

CONFIDENTIAL

This material is the property of the NYU School of Medicine and Langone Medical Center. Do not disclose or use except as authorized in writing by the study sponsor

Medical History			X
Physical Exam			X
Height			X
Weight			X
Vitals signs			X

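### The consent point is stated two ways and the primary endpoint has no denominator, so the feasibility result can leave out transplanted patients who never converted by day 30

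*Combined protocol and SAP*

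**What the plan says.** **Objective and endpoint.** Section 3.1: "The primary objective will be to assess the feasibility of early conversion to Envarsus XR at 1-year follow-up". Section 4.2.1: "The primary endpoint will be percentage of patients remaining on Envarsus XR at 1-year follow-up". Section 10.4.2 says of this endpoint only that "It will be analyzed using descriptive statistics"; it names no analysis set.

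**Consent.** Section 5.4: "Written informed consent for enrollment in the study will occur once the patient has been listed for lung transplantation". It adds that the interval from consent to transplant will vary. The Schedule of Events puts the consent row and the eligibility review under "Screening Visit (POD 0 to30" days, and lets first dispensation fall on the same day. Section 14.1 describes the enrolment window as the first 30 days after transplant.

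**Eligibility.** In the prospective arm, criterion 2 is having received the transplant, and criterion 3 is "Be able to convert to Envarsus XR within the first month post-transplant".

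**Analysis sets.** Section 10.3 defines two: patients with at least one dose, for safety, and patients completing the first post-transplant year, for efficacy (called per-protocol). Neither is linked to the primary endpoint.

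**Target of 40.** Section 5.4 describes these as patients with early conversion. Section 5.6 says "Forty patients are expected to be enrolled and switched to Envarsus XR post-transplant". Section 10.5 takes the number from the transplants expected in one year, with no power calculation.

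**The concern.** A feasibility study of early conversion has to count the patients in whom early conversion was not achieved. Here, being able to convert is a condition of entry. It cannot be known at listing, so it has to be judged after transplant, possibly on the day of first dispensation. A transplanted patient who could not be converted within the month can then be classed as ineligible instead of as a feasibility failure, and nothing later in the plan brings that patient back into the count.

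The unclear consent point makes this worse. If consent is taken at listing, there is an identifiable group of consented and transplanted patients against which conversion can be measured. If it is taken after transplant, possibly on the day of first dispensation, patients who do not convert may never be consented, and the study may hold no record of them. The consent date also fixes when reportable events start to be recorded, because Section 8.3 counts from "any time after informed consent is obtained".

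**Working it through.** **Step 1. Which denominators the text allows.** The plan gives no figure for the primary endpoint to reproduce. The only sample-size arithmetic is 40 / 20 = 2, the stated 2:1 ratio. The possible denominators are:

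| Denominator | Source | Includes a transplanted patient never converted by day 30? |
|---|---|---|
| Consented at listing and transplanted | 5.4 | Yes |
| Enrolled at day 0–30 under criterion 3 | 5.1, 14.1, Section 20 | No, if criterion 3 is applied then |
| At least one dose | 10.3, safety set | No, if no dose was ever taken |
| Completed the first year | 10.3, efficacy set | No, if never entered or never dosed |

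Only the first necessarily counts a failure to convert.

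**Step 2. Illustration with the target read as 40 converted patients.** The documents give no rate of non-conversion or of stopping, so these counts are assumptions: 34 of the 40 are still on drug at 1 year, and 0, 4 or 8 further consented and transplanted patients never converted.

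Proportion = x / n. The exact (Clopper-Pearson) 95% limits are the 0.025 quantile of Beta(x, n − x + 1) and the 0.975 quantile of Beta(x + 1, n − x).

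- None unconverted: 34 / 40 = 85.0% (70–94%).
- 4 unconverted: n = 40 + 4 = 44; 34 / 44 = 77.3% (62–89%).
- 8 unconverted: n = 40 + 8 = 48; 34 / 48 = 70.8% (56–83%).

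Among converted patients the figure stays at 85.0% however many patients fail to convert, so it carries no information on conversion.

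**Step 3. Illustration with the target read as 40 consented and transplanted patients.** Assume 8 never convert, 4 convert and later stop, and 2 converted patients die or withdraw before 1 year. Still on drug: 40 − 8 − 4 − 2 = 26.

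- All consented and transplanted: 26 / 40 = 65.0% (48–79%).
- At least one dose: n = 40 − 8 = 32; 26 / 32 = 81.3% (64–93%).
- Completed year 1: n = 40 − 8 − 2 = 30; 26 / 30 = 86.7% (69–96%).

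Keeping 4 stops and 2 deaths or withdrawals, and varying only the number never converted:

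| Never converted | On drug / consented and transplanted | On drug / at least one dose |
|---|---|---|
| 0 | 34/40 = 85.0% | 34/40 = 85.0% |
| 4 | 30/40 = 75.0% | 30/36 = 83.3% |
| 8 | 26/40 = 65.0% | 26/32 = 81.3% |
| 12 | 22/40 = 55.0% | 22/28 = 78.6% |

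From 0 to 12 failures the first column falls by 30 percentage points (85.0 − 55.0) and the second by 6.4 (85.0 − 78.6).

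**The case against.** The strongest reply is that the intended denominator can be inferred. A patient can only remain on a drug already started, the target is described as patients converted or switched, and study day 0 is first dispensation. All of this points to converted patients. The objective is also framed at 1 year, which a persistence measure can partly serve. In addition, the endpoint is descriptive, no test or threshold depends on it, and the failure counts above are assumed.

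Much of this stands. Converted patients are the most natural reading, and the size of the effect is unknown. But that reading confirms the difficulty: the percentage would then say nothing about how often early conversion could be achieved. Nor is it secured by the text, since 10.4.2 names no set and its heading calls the endpoint an efficacy endpoint, for which 10.3 prescribes year-1 completers.

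Four stronger inferences should not be drawn.

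- A reader might infer that 5.4 contradicts 14.1. It does not: consent at listing followed by enrolment within 30 days after transplant is coherent, and criterion 2 cannot be met before transplant anyway. The conflict is between 5.4 and the consent row of the schedule. Consent at listing with reconfirmation at screening would resolve it, but the documents do not say so.
- A reader might infer that every failed conversion is lost. Patients who convert and later return to immediate-release tacrolimus are not removed by criterion 3 or by a one-dose denominator; there they count as not remaining on drug. They would drop out only if the completer set were applied and completion were read as completion on drug, which 10.3 leaves open.
- A reader might infer that the halt on any patient death in 10.4.7.1 moves with the consent date. That section does not mention consent.
- A reader might assume that a consent log already supplies the counts. Section 13.3.2 describes documentation in each subject's research record and names no log.

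**Conclusion.** The point holds for patients never converted within the first month. Criterion 3 makes the thing being studied a condition of entry, no denominator is stated, and neither set in 10.3 would restore the patients left out. Followed as written, the plan can report persistence among converters under the name of feasibility of early conversion. That conclusion rests on the text and needs no assumed rate.

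The size does rest on assumptions. With 34 patients on drug, 4 or 8 unconverted patients lower the figure from 85% to 77% or 71%. If there are none, the figures for converted patients and for consented and transplanted patients agree. The intervals overlap widely at this sample size; the difference is one of what is being estimated, not of statistical significance.

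The consent discrepancy is a separate, smaller matter of wording, but until it is settled the population of consented and transplanted patients cannot be defined.

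**What to change.** 1. State one consent point in 5.4 and Section 20. If consent is at listing and reconfirmed at screening, say so. Section 14.1 can keep its post-transplant enrolment window.
2. Treat conversion by day 30 as an outcome, not as a condition for being counted, and align criterion 3 in 5.1 with this.
3. In 4.2.1, 10.3 and 10.4.2, name the denominator as all consented and transplanted patients. This leaves out patients who consent at listing and are never transplanted. Report with exact 95% confidence intervals (a) the percentage converted by day 30 and (b) the percentage on Envarsus XR at 1 year. Keep the percentage on drug at 1 year among converted patients as a supporting figure.
4. State how deaths and withdrawals before 1 year count in each figure.
5. Say in 5.4, 5.6 and 10.5 whether the 40 are consented and transplanted patients or converted patients.

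The statistical work is only counting. The costs are a protocol amendment, the tracking of consented and transplanted patients who never convert, a possible effect on how the target of 40 is reached, and a headline percentage that may be lower.
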